## 1. STUDY SYNOPSIS

Name of Sponsor/Company: Topical Remedy, LLC	Individual Study Table Referring to Part of the Dossier  Volume:	(For National Authority Use only)
Name of Finished Product: Merlin		
Name of Active Ingredient: Ethanol and Glycolic Acid	Page:	
Title of Study: A Multicenter, Placebo-Controlled, Randomized, Double-Blind Study of the Safety and Efficacy of Merlin (ethanol and glycolic acid mixture) for the Episodic Treatment of Recurrent Herpes Labialis		
Study Centers: There will be approximately 5 - 10 study centers.		
Publication (reference): Not applicable		
Study Duration: Approximately 9 months		
Objectives: The primary efficacy endpoint of this study is the clinician assessed duration of the classical lesion.		
Methodology: This is a multicenter, randomized, double-blind, placebo-controlled study to evaluate the safety and efficacy of Merlin (10 % ethanol and 0.6% glycolic acid) for the treatment of herpes labialis lesions. Subjects who meet the eligibility requirements at the screening/randomization visit will be randomized in a 1:1 ratio to one of two treatment groups: 1) twelve (12) treatments with Merlin solution, administered 6 hours apart (up to 3 per day) over the ensuing 96 hours (4 days) from the time of the first treatment; or 2) twelve (12) treatments with 10% ethanol, as a placebo, administered 6 hours apart (up to 3 per day) over the ensuing 96 hours (4 days) from the time of the first treatment. Each treatment of Merlin or placebo consists of applying the solution three (3) times, within a time period of 40 minutes or less, while allowing time for the solution to dry on the lesion between applications; this will result in a total of thirty six (36) applications over 96 hours (4 days). The first treatment will be administered on Treatment Day (Day 0), and then repeated at 6 and 12 hours after the first treatment, time permitting.		

Name of Sponsor/Company: Topical Remedy, LLC	Individual Study Table Referring to Part of the Dossier	(For National Authority Use only)
Name of Finished Product: Merlin	Volume:	
Name of Active Ingredient: Ethanol and Glycolic Acid	Page:	

**Methodology (cont.):**

After being enrolled and randomized into the study, subjects will be sent home with a kit containing a bottle filled with either Merlin (active) or the 10% ethanol placebo solution and a packet of foam-tipped applicators sufficient to apply three (3) study treatments (nine (9) applications). The subject will be instructed to contact the clinic by telephone at the first signs and/or symptoms of a recurrent herpetic episode (Stage 0, prodrome, Stage 1, erythema, or Stage 2, papule/edema). The lesion and lesion stage then will be confirmed by telephone interview with the subject. Subjects reporting either a Stage 1 or Stage 2 lesion will be instructed to begin treatment immediately, thereby initiating the Treatment Phase of the study. Subjects reporting only Stage 0 symptoms, i.e. no visible signs of a cold sore lesion, will be instructed to monitor their lesion and to call the clinic immediately upon observing any early visible signs of a cold sore, i.e. redness or swelling, representing a Stage 1 or Stage 2 lesion. Once the subject calls in and confirms by telephone interview that their lesion has reached Stage 1 or 2, they will be instructed to begin treatment immediately. The subject will be told to continue treatment for the remainder of the day with the treatment schedule outlined above, and to continue to treat with a set of three (3) applications, three (3) times each day, for a total of twelve (12) treatments resulting in thirty-six (36) applications in total. The subject also will be instructed to return to the clinic within 24 hours of the initial treatment for evaluation of the stage of the herpetic lesion.

Subjects will report daily for a minimum of 3 consecutive days, with the last clinic visit at the time of complete healing (Stage 7 - normal skin) or at 14 days, whichever is earlier. Subjects will be contacted by phone, for a safety assessment, 2 weeks after they complete the Treatment Phase of the study.

**Number of Subjects:** Approximately four hundred and fifty (450) subjects will be enrolled into the study, 225 into the active treatment group and 225 into the placebo treatment group. At least 75 subjects in the active treatment group, and 75 subjects in the placebo treatment group, will enter the Treatment Phase of the study and administer treatments.

**Diagnosis and Main Criteria for Inclusion:** All enrolled subjects must be 18 to 75 years of age. To be enrolled, he or she must also have a history of recurrent herpes labialis and report at least 3 recurrences during the preceding 12 months. To enter the Treatment Phase of the study, the subject must have a herpes labialis lesion assessed by the subject and confirmed by telephone contact to be at either Stage 1 (erythema) or Stage 2 (papule/edema), and the subject must be able to report to the clinic for an initial lesion assessment within 24 hour of detection of first signs and/or symptoms of a herpetic episode. The subject must also be able to report to the clinic for up to 14 days.

Name of Sponsor/Company: Topical Remedy, LLC	Individual Study Table Referring to Part of the Dossier  Volume:  Page:	(For National Authority Use only)	
Name of Finished Product: Merlin			
Name of Active Ingredient: Ethanol and Glycolic Acid			

Test Product and Mode of Administration: Merlin is the name given to a novel formulation intended for the treatment of topical viral infections. The formulation consists of 10% ethanol and 0.6% glycolic acid, with a pH of 2.5. A single-use, foam-tipped applicator will be used for application to the skin.
 
Duration of Treatment: Each subject, for each set of treatments, will administer three (3) applications of Merlin or placebo, depending upon how a subject has been randomized, within a time period of 40 minutes or less, while allowing time for the solution to dry on the lesion between applications. A total of twelve (12) Merlin treatments, i.e. thirty-six (36) applications, will be administered over the ensuing 96 hours (four (4) days), following the time of the first treatment. On each day, treatments will be administered six (6) hours apart, with a maximum of three (3) treatments each day. The first treatment will be administered on Treatment Day (Day 0), and then repeated at 6 and 12 hours after the first treatment, time permitting.
			

Reference Therapy, Dose and Mode of Administration: The reference therapy will be a set of three (3) applications of 10% ethanol, applied twenty (20) minutes apart with the same dosing schedule as outlined above in "Duration of Treatment."
 
Criteria for Evaluation: The primary efficacy endpoint is the clinician assessed duration of the classical herpetic lesion.
 
Secondary efficacy endpoints are as follows:
 
 
• Clinician assessed duration of the herpetic episode
 
• Clinician assessed duration of complete healing of the herpetic episode
 
• Clinician assessed prevention of progression to a classical lesion
 
• Clinician assessed lesion size (maximum lesion area; cumulative lesion area)
 
• Clinician assessed duration of the herpetic lesion hard scab
 
 
Based on patient diary entries, other efficacy endpoints will be:
 
 
• Subject assessed duration and severity of lesion pain
 
• Subject assessed duration of the classical herpetic lesion
 
• Subject assessed duration of the herpetic episode
 
• Subject assessed duration of complete healing of the herpetic episode
 
• Subject assessed prevention of progression to a classical lesion
 
• Subject assessed duration of the herpetic lesion hard scab
 
 
The only safety endpoint is adverse events.
			

Name of Sponsor/Company: Topical Remedy, LLC	Individual Study Table Referring to Part of the Dossier	(For National Authority Use only)
Name of Finished Product: Merlin	Volume:	
Name of Active Ingredient: Ethanol and Glycolic Acid	Page:	

Statistical Methods: Generally, statistical hypothesis tests will be two-tailed, and statistical significance will be declared when the p-value is less than 0.05. Continuous variables will be summarized using descriptive statistics, specifically the mean, median, standard deviation, minimum and maximum. Categorical variables will be summarized by frequencies and percentages.
 
All subjects who received (at least some) treatment, whether they were formally entered into the Treatment Phase of the study or applied the test material without formal authorization, will be included in the Safety Population. The safety analysis will be performed on the Safety Population.
 
All subjects who have been entered into the Treatment Phase of the study will be included in the Modified Intent to Treat (MITT) population. The MITT population will be used as the primary analysis population. All subjects who have been entered into the Treatment Phase of the study and have been followed successfully until their lesion healed, or until 14 days, whichever is earlier, will be included in the Efficacy Evaluable population. The efficacy analysis will be performed on both the MITT and the Efficacy Evaluable populations.
 
No imputation of missing data will be performed for the efficacy analyses for the Efficacy Evaluable population.
 
The duration of the classical herpetic lesion (both clinician and patient assessed) will be analyzed using the Hodges-Lehmann method as the primary efficacy analysis method for estimating the median difference between the two arms. Duration of the herpetic episode (both clinician and patient assessed), duration of complete healing of the herpetic episode (both clinician and patient assessed), duration of the herpetic lesion (both clinician and patient assessed), duration of the herpetic lesion hard scab (both clinician and patient assessed), and duration of pain will be analyzed in the same manner as the duration of the classical lesion.
 
The proportions of subjects in each treatment group who do not display classical lesions (prevention of progression to classical lesions) will be compared using Fisher's Exact Test.
 
For pain, the maximum severity will be analyzed using the Cochran-Mantel-Haenszel Test to test for differences between treatment groups.
		

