The results of this study found that twelve (12) treatments with Merlin solution, administered 6 hours apart (up to 3 per day) over 96 hours, was generally safe and tolerable in the treatment of subjects with lesions associated with herpes simplex labialis. The majority of treatment-related AEs were classified as mild in intensity. No treatment related AEs in any cohort were classified as severe.

An a priori analysis found that those subjects, who treated with Merlin at first visible signs of a herpetic lesion, erythema, rather than immediately at first symptoms of a herpetic lesion, the prodromal stage, exhibited statistically significant efficacy as compared to placebo for the duration of the classical lesion. The same a priori analysis found trends towards significance for the endpoints of complete healing, duration of the herpetic episode, cumulative lesion size, duration of the hard scab, and the subject assessed severity of lesion pain.

This current clinical study is a follow-up Phase 2 trial using the same Merlin formulation as was used in the studies described above. This trial, as the previous Phase 2 study, will have two treatment arms comparing the safety and efficacy of Merlin solution to that of a placebo (10% ethanol) with treatment at first visible signs of a herpetic episode.

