#### **10.7.9 Sample Size Determination**

The sample size for this study was based upon the results of the previous Phase 2 study, TR-H-211. In that study, Merlin demonstrated a statistically significant ( $p=0.0276$ ) effect on the duration of classical lesion endpoint for subjects beginning treatment at Stage 1 (erythema) with only 32 subjects treated with Merlin and 22 placebo subjects. Clinical investigations with Famvir and other independent studies, that initiate treatment within hours of the onset of prodromal symptoms (Stage 0) have demonstrated that 1/3 of all subjects enrolled in herpes labialis studies will have spontaneously aborted lesion. Any calculation of clinical trial size, therefore, must consider that factor. When, however, treatment is initiated at the erythema stage (Stage 1), as in the Merlin Phase 2a (TR-H-211) study, the incidence of spontaneously aborted lesions declines to 25%. As a result, a larger percentage of subjects will demonstrate classical lesions in Merlin studies than was seen in the Famvir, or similar previous studies. This was factored in when performing

power calculations for this Phase 2b clinical study. Those calculations determined that 144 subjects would provide a 95% likelihood of statistical significance for the herpetic episode endpoint. Merlin decreased the duration of herpetic episode in subjects that began treatment at stage 1 by 41 hours, with a p-value of 0.055 in the Phase 2a study. The herpetic episode endpoint includes the subjects with aborted lesions.

As a result, a 150 subject clinical trial will have approximately 60 subjects progress to classical lesions in each treatment arm and we can be highly confident of having the power to demonstrate a highly significant difference for the duration of classical lesion endpoint, as shown in the Phase 2a results. In addition, a 150 subject clinical trial should have greater than 95% likelihood of demonstrating a statistically significant Merlin effect on herpetic episode as a secondary endpoint.

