## 6 Study Endpoints

### 6.1 Efficacy Endpoints

#### 6.1.1 Primary Efficacy Endpoint

The primary efficacy endpoint is the clinician assessed duration of the classical herpetic lesions.

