#### 6.1.2 Secondary Efficacy Endpoints

The secondary efficacy endpoints include:

- clinician assessed
  - duration of the herpetic episode (classical and non-classical)
  - duration until complete healing of the herpetic episode (classical and non-classical)
  - prevention of progression to a classical lesion
  - maximum lesion area of the classical lesions
  - cumulative lesion area of the classical lesions
  - cumulative lesion area of all lesions
  - duration of classical herpetic lesion hard scab

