#### 6.1.3 Other Efficacy Endpoints

Based on patient diary entries, the other efficacy endpoints include:

- subject assessed:
  - duration of the classical herpetic lesion
  - duration of the herpetic episode (classical and non-classical)
  - duration of complete healing of the herpetic episode (classical and non-classical)
  - prevention of progression to a classical lesion
  - duration of classical herpetic lesion hard scab
  - severity of lesion pain
  - duration of lesion pain

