## **7.2 General Analysis**

All statistical tests will be done using two-sided tests and a Type I error rate of 0.05.

Data listings will be based on all subjects in the Safety Population.

Continuous variables will be summarized using descriptive statistics, specifically the mean, median, standard deviation, minimum and maximum values. Categorical variables will be summarized by frequencies and percentages.

The primary analyses will compare the active treatment group to the placebo control group. Aside from any placebo effect, there should be no efficacy associated with the placebo solution. In addition to the overall analyses, all statistical comparisons will be performed with the subjects stratified based on whether they were treated at erythema (Stage 1) or papule/edema (Stage 2). Inference testing will be completed on efficacy data to compare the groups. Safety data will be summarized with descriptive statistics, but no inference testing will be completed to compare the groups statistically.

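### Beyond the primary test, secondary endpoints can be declared significant at p<0.05 with no gate and no nominal label; for an inactive drug, about a 23% chance of at least one if the tests correlate at 0.5 (11% to 30% over the range tried)

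*Protocol*

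**What the plan says.** **Primary.** SAP 6.1.1 states: "The primary efficacy endpoint is the clinician assessed duration of the classical herpetic lesions". Protocol 10.3.2 and SAP 7.1.2 make MITT the primary population. Protocol 10.7 and SAP 7.13.5 name one main MITT analysis for durations.

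**Decision rule.** The Protocol synopsis (Statistical Methods) says that "statistical significance will be declared when the p-value is less than 0.05", in a sentence that opens with the word *Generally*. SAP 7.2, like Protocol 10.4, says: "All statistical tests will be done using two-sided tests and a Type I error rate of 0.05". SAP 7.2 adds: "Inference testing will be completed on efficacy data to compare the groups".

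**Endpoints tested.** Under "The secondary efficacy endpoints include", SAP 6.1.2 lists seven: episode duration, complete healing, prevention of progression, maximum area (classical), cumulative area (classical), cumulative area (all lesions) and hard scab duration. Under "Based on patient diary entries, the other efficacy endpoints include", SAP 6.1.3 lists seven more. The Protocol synopsis has five secondary bullets (six variables), and Protocol 10.2.1 has a different set of six bullets.

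**Repeats.** SAP 7.13 and 7.13.5 repeat the tests in MITT and EE, overall and by Stage 1 and Stage 2. SAP 7.13 also compares groups at each visit where the endpoint is captured.

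**Intended use.** Protocol 10.7.9, matched in SAP 3, says that 150 subjects should give "greater than 95% likelihood of demonstrating a statistically significant Merlin effect on herpetic episode as a secondary endpoint".

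Neither document gives a testing order, an alpha split, a condition on the primary, or a statement that any endpoint is exploratory or nominal.

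**The concern.** The words primary, secondary and other sort the endpoints, but they have no stated consequence for what may be declared. Followed as written, the trial could miss its primary and still report Merlin as significantly better on episode duration, healing, progression, any of three area measures or hard scab. The error rate attached to that kind of statement is not the 0.05 the plan prints. A reader of the report could not separate a controlled secondary claim from a chance finding.

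This is more than a missing detail, because the sample size sections plan a significance claim on one secondary and do not make it depend on the primary.

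**Working it through.** **1. The plan's own figure.** No family-wise rate is given. The one power statement is 144 subjects for 95% on episode duration, based on a 41-hour difference with p = 0.055 (Protocol 10.7.9). No SD is printed. Taking the printed 32 and 22 as the analysed group sizes:

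- z for two-sided p = 0.055 is 1.919. SD = 41 / (1.919 × √(1/32 + 1/22)) = 77.1 h.
- With 72 per arm, 41 / (77.1 × √(2/72)) = 3.19. Two-sided power = Φ(3.19 − 1.96) = 0.89.

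So 95% is not reproduced at two-sided 0.05. A one-sided 0.05 test gives 0.94. This does not affect the multiplicity point, but it explains why step 4 starts from about 90%.

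**2. Chance of at least one false secondary.** Inputs: k = 7 (SAP 6.1.2), two-sided 0.05 each, inactive drug, MITT overall analysis only. If independent, 1 − 0.95^7 = 0.302. In favour of Merlin only, 1 − 0.975^7 = 0.162. With a common correlation ρ between test statistics and c = 1.96:

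1 − ∫ [Φ((c − √ρ·x)/√(1−ρ)) − Φ((−c − √ρ·x)/√(1−ρ))]^7 φ(x) dx

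The Merlin-favouring version drops the second Φ.

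| Correlation (assumed) | Any of 7, either direction | Any of 7, favouring Merlin |
|---|---|---|
| 0 | 0.302 | 0.162 |
| 0.5 | 0.230 | 0.115 |
| 0.8 | 0.149 | 0.074 |
| 0.9 | 0.114 | 0.057 |

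The single-test benchmarks are 0.05 and 0.025. At correlation 0.5 both ratios are 4.6 (0.230/0.05 and 0.115/0.025).

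**3. Sensitivity.**

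- *Count.* Using five tests (the synopsis bullets) gives 0.226 if independent, 0.183 at 0.5 and 0.102 at 0.9. Six tests give 0.265, 0.207 and 0.108.
- *Dependence.* An illustrative null simulation of the seven SAP endpoints (75 per arm, 75% classical, 3,000 trials, assumed stage durations) gave 22.4% for any significant secondary. In 19.1% of trials this came with a non-significant primary.
- *Not counted.* EE, by-stage and by-visit repeats are left out and would raise these figures.

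**4. Cost of a gate.** The effective size in Phase 2a is 32 × 22 / 54 = 13.04.

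- Primary: p = 0.0276 gives z = 2.203. Classical lesions per arm: 75 × 0.75 = 56, so the effective size is 28. Expected z = 2.203 × √(28/13.04) = 3.228; power = Φ(3.228 − 1.96) = 0.898.
- Episode: z = 1.919 with 75 per arm, effective size 37.5. Expected z = 1.919 × √(37.5/13.04) = 3.254; power = Φ(3.254 − 1.96) = 0.902.
- Both significant (bivariate normal): 0.83 at correlation 0.5, 0.86 at 0.8, 0.87 at 0.9.

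**The case against.** **The trial's own question is safe.** One endpoint, one population and one main analysis carry the primary conclusion at 5%. This is a Phase 2 trial, and no section says that a secondary result would count as trial success. This stands, and it limits the point to what may be declared beyond the primary. It does not remove the point, because the plan itself forecasts a significant secondary.

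**There are tiers.** The documents separate primary, secondary and other endpoints, and Protocol 10.4 calls the by-stage comparisons a secondary analysis. This also stands: what is missing is a testing rule, not a ranking. Adding the diary endpoints to reach fourteen tests (0.35 at correlation 0.5) would treat the lowest tier as claims, so the size given here rests on the seven secondaries.

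**The decision rule is softer than it looks.** The declaring sentence appears only in the synopsis and is qualified by *Generally*. Protocol 10.4 and SAP 7.2 only set the level. That is fair, but nothing in either document says where the general rule does not apply.

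**23% is not a documented figure.** Correct. It needs a correlation of 0.5, which the documents do not give, and it includes results favouring placebo. A reader might infer that false claims for Merlin run at several times 0.05. Set against 0.05, the Merlin-favouring figures are only 1.1 to 3.2 times as large. The proper benchmark for one direction is 0.025.

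**Phase 2a history.** A reader might infer that the programme has already built on an uncontrolled secondary, because TR-H-211 had complete healing as its primary objective and carried forward a result on classical lesion duration. The documents do not support that. Protocol 2 calls the analysis a priori, the TR-H-211 plan is not available, and the sponsor is retesting the endpoint as the single primary of a new randomised trial.

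**Conclusion.** The point holds in a limited form. The primary test is sound. The plan's general rule lets each of seven secondary endpoints be declared significant at 0.05 whether or not the primary succeeds, and it forecasts such a claim for episode duration.

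For an inactive drug, the chance of at least one significant secondary is about 23% at correlation 0.5, with a range of 11% to 30%. In Merlin's favour it is about 11.5%, with a range of 6% to 16%, against 2.5% for one test. The correlations are assumptions. The conclusion does not depend on them: even at 0.9 the rate is more than twice the single-test level (0.114/0.05 = 2.3). Nor does it depend on taking the SAP count of seven over the synopsis count.

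This should be corrected before unblinding. It does not threaten the validity of the primary result.

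**What to change.** In the Protocol synopsis, Protocol 10.4 and SAP 7.2 and 7.13, replace the general rule with the following, for the MITT main analysis:

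1. Test the primary at two-sided 0.05.
2. Only if it is significant, test clinician assessed herpetic episode duration at two-sided 0.05. It is the one secondary for which the plan states a power.
3. Report all other secondaries, all diary endpoints, and all EE, by-stage and by-visit repeats with estimates, 95% confidence intervals and nominal p-values, not declared significant.

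If the sponsor wants claims on more secondaries, apply Holm across them after the primary succeeds (first step 0.05/7 = 0.0071 if all seven are included). Either way, an inactive drug has at most a 5% chance of any false declared claim.

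A fixed sequence through all seven in SAP order is less suitable. Prevention of progression would come third. With 75 per arm and 25% aborted lesions on placebo, its power is only about 16% to 50% for assumed Merlin rates of 32% to 40%. It would often block cumulative area and hard scab.

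In Protocol 10.7.9 and SAP 3, state that the episode claim depends on the primary succeeding.

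**Cost.** Only wording changes, and SAP 9 allows amendment before unblinding. No new data, subjects or analyses are needed. The chance of an episode claim falls from about 90% to about 83-87%, on the printed Phase 2a p-values with 32 and 22 as the analysed sizes. The other secondaries become supportive only.
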